	Days -28 to -1	Day 1 ^c	Day 8 for Part D1 only (± 1 day)	Day 15 (± 2 days)	Day 29 (± 2 days)	Period 2 Visit ^d		
Informed consent	X							
Randomization ^e		X						
Demographics	X							
Medical history	X							
CFQ-R ^{f,g}		X		X	X			
Weight ^h	X	X	X	X	X		X	
Height ^h	X							
Vital signs ⁱ	X	X	X	X	X	X	X	
Pulse oximetry ⁱ	X	X	X	X	X	X	X	

^a All assessments will be performed before dosing, unless noted otherwise. Assessments that are collected before and after dosing will only be collected once if study drug is not administered on the day of the visit (i.e., if subject prematurely discontinued study drug treatment).

^b If the subject prematurely discontinues study drug treatment, an ETT Visit should be scheduled as soon as possible after the decision to terminate study drug treatment. Subjects who prematurely discontinue treatment will be required to complete the Safety Follow-up Visit. If the ETT Visit occurs 3 or more weeks after the last dose of study drug, the ETT Visit will replace the Safety Follow-up Visit, and a separate Safety Follow-up Visit will not be required.

^c To be eligible to continue into the Treatment Period, subjects must have stable CF disease and have remained on stable CF medication regimen during the 28 days before the Day 1 Visit AND must not have had an acute non-CF illness within 14 days before the Day 1 Visit. See [Section 9.1.2.4](#).

^d The Period 2 Visit will occur 6 to 10 days after the actual date of the Day 29 Visit.

^e Randomization may occur on the previous day (Day -1 Visit) after all inclusion and exclusion criteria have been confirmed.

^f CFQ-R must be completed before the start of any other assessments scheduled at that visit.

^g The predose assessment on the Day 1 Visit may be performed on the previous day (Day -1 Visit) if randomization has occurred.

^h Weight and height will be measured with shoes off.

ⁱ Vital signs and pulse oximetry will be collected after the subject has been seated for at least 5 minutes.

Table 3-6 Study VX16-445-001: Schedule of Assessments for Parts D1 and D2

Event/Assessment ^a	Screening	Treatment Period					ETT Visit ^b	Safety Follow-up 28 (± 7) Days After Last Dose
		Period 1			Period 2			
	Days -28 to -1	Day 1 ^c	Day 8 for Part D1 only (± 1 day)	Day 15 (± 2 days)	Day 29 (± 2 days)	Period 2 Visit ^d		
Physical examination ^j	Complete	Abbrev.		Abbrev.	Abbrev.		Abbrev.	Complete
Standard 12-lead ECG ^k	X	X	X	X	X		X	X
Sweat chloride ^{g,l}	X	X	X	X	X	X ^m	X	X

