^v On days of scheduled visits, the in-clinic dose of study drugs will be given in the morning, at least 6 hours apart from any other scheduled dose and after all predose assessments are complete. The last dose of VX-445 or placebo in Period 1 will be the morning dose on the Day 29 Visit. See [Section 9.6.2](#) for additional information about study drug administration.

^w Refer to [Section 9.5.2](#) for details.

Table 3-7 Study VX16-445-001: Schedule of Assessments for Part E

Event/Assessment ^a	Screening	Run-in Period		Treatment Period: Period 1			Washout Period		ETT Visit ^b	Safety Follow-up 28 (± 7) Days After Last Dose ^c
	Days -56 to -29	Day -28 (± 1 day)	Day -14 ^d (+ 13 days)	Day 1 ^e	Day 15 (± 2 days)	Day 29 (± 2 days)	Day 43 (± 3 days)	Day 57 (± 3 days)		
Informed consent	X									
Randomization ^f				X						
Demographics	X									
Medical history	X									
CFQ-R ^{g,h}				X	X	X		X		
Weight ⁱ	X	X		X	X	X	X	X	X	X
Height ⁱ	X									
Vital signs ^j	X	X		X	X	X	X	X	X	X
Pulse oximetry ^j	X	X		X	X	X	X	X	X	X
Physical examination ^k	Complete	Abbreviated		Abbreviated	Abbreviated	Abbreviated		Abbreviated	Abbreviated	Complete

^a All assessments will be performed before dosing, unless noted otherwise. Assessments that are collected before and after dosing will only be collected once if study drug is not administered on the day of the visit (i.e., if subject prematurely discontinued study drug treatment).

^b If the subject prematurely discontinues study treatment, an ETT Visit should be scheduled as soon as possible after the decision to terminate study drug treatment. Subjects who prematurely discontinue treatment will also be required to complete the Safety Follow-up Visit. If the ETT Visit occurs 3 weeks or later following the last dose of study drug, the ETT Visit will replace the Safety Follow-up Visit, and a separate Safety Follow-up Visit will not be required. Part E subjects who meet criteria specified in [Section 9.1.2.6](#) will not have a Safety Follow-up Visit.

^d The Day -14 Visit is only required for subjects who are not transitioning directly from at least 14 days of uninterrupted TEZ/IVA treatment. Assessments at this visit may be performed postdose.

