VX-445/TEZ/VX-561 or placebo dosing ^t		Day 1 through Day 29					
AEs, medications ^u , treatments, and procedures	Continuous from signing of the ICF through the Safety Follow-up Visit						

AE: adverse event; CF: cystic fibrosis; CFQ-R: Cystic Fibrosis Questionnaire-Revised; *CFTR*: CF transmembrane conductance regulator gene; ████████████████████ ECG: electrocardiogram; ETT: early termination of treatment; FSH: follicle-stimulating hormone; G6PD: glucose-6-phosphate dehydrogenase; ICF: informed consent form; IVA: ivacaftor; PE: physical examination; PK: pharmacokinetic; ppFEV₁: percent predicted forced expiratory volume in 1 second ; TEZ: tezacaftor

- ^s Blood samples will be collected for PK analysis of VX-445, TEZ, M1-TEZ, and VX-561. On the Day 1 Visit, samples will be collected before dosing (0 hours) and at 1, 2, 4, and 6 hours after dosing (relative to the morning dose). On the Day 15 Visit, samples will be collected before dosing (0 hours) and at 1, 2, 4, 6, and 8 hours after dosing. On the Day 29 Visit, a predose sample will be collected before the morning dose of study drug. At the ETT visit, a single blood sample for PK analysis will be collected.
- ^t On days of scheduled visits, the in-clinic dose of study drugs will be given in the morning, at least 6 hours apart from any other scheduled dose and after all predose assessments are complete. The last dose of VX-445/TEZ/VX-561 or placebo will be the morning dose on the Day 29 Visit. See [Section 9.6.2](#) for additional information about study drug administration.
- ^u Refer to [Section 9.5.2](#) for details.

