Coagulation Vital Signs (including Weight) Pulse oximetry	Day 1 (Baseline) Day 15 Day 29 Safety Follow-up	1 15 29 57	≤1 Pre-dose [1,22] (22, 43] Use nominal visit
Standard 12-Lead ECG	Day 1 (Baseline; before dosing) Day 1 (5 hours after dosing) Day 15 (before dosing and 5 hours after dosing) Day 29 Safety Follow-up	1 1 15 29 57	Use nominal visit for all visits
Spirometry	Day 1 (5 hours post dose) Day 15 (5 hours post dose)	1 15	Use nominal visit Use nominal visit
Efficacy Assessment (Parts D1 and D2)			
Spirometry Sweat Chloride	Day 1 (Baseline) Day 8 (Part D1) Day 15 (Part D1) Day 15 (Part D2) Day 29 Period 2 visit Safety Follow-up	1 8 15 15 29 Period 2 visit (36) 64	≤1 Pre-dose (1, 12] (12, 22] (1, 22] (22, 33] (33, 50] Use nominal visit
CFQR	Day 1 (Baseline) Day 15 Day 29	1 15 29	≤1 Pre-dose (1, 22] (22, 47]
Efficacy Assessment (Part E)			

Table 11-4 Analysis Visit Windows for Safety and Efficacy Assessments			
Assessment	Visit^a	Target Study Day^b	Analysis Visit Window (in study days)
Spirometry	Day 1 (Baseline)	1	≤1 Pre-dose
	Day 15	15	(1,22]
	Day 29	29	(22, 36]
	Day 43	43	(36, 50]
	Day 57	57	(50, 71]
	Safety Follow-up	85	Use nominal visit
Sweat Chloride	Day 1 (Baseline)	1	≤1 Pre-dose
	Day 15	15	(1,22]
	Day 29	29	(22, 36]
	Day 43	43	(36, 50]
	Day 57	57	(50, 71]
CFQR	Day 1 (Baseline)	1	≤1 Pre-dose
	Day 15	15	(1,22]
	Day 29	29	(22, 43]
	Day 57	57	(43, 71]
Efficacy Assessment (Part F)			
Spirometry Sweat Chloride	Day 1 (Baseline)	1	≤1 Pre-dose
	Day 15	15	(1,22]
	Day 29	29	(22, 43]
	Safety Follow-up	57	Use nominal visit
CFQR	Day 1 (Baseline)	1	≤1 Pre-dose
	Day 15	15	(1,22]
	Day 29	29	(22, 43]

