
Notes:
 
The analysis visit windows will be applied using the following rules for both scheduled and unscheduled visits:
 
 1. If no numerical measurement is available within a visit window, the measurement will be considered missing for the visit. 2. If there is more than 1 numerical measurement available within the same visit window, use the following rules: 
 a. For efficacy parameters: if there are multiple measurements within a visit window, the measurement at the scheduled visit will be used. Otherwise, 
 i. If there are no measurements at the scheduled visit, then the measurement closest to the target day will be used; or ii. If there are multiple measurements with the same distance to the target day, the latest measurement will be used. b. For safety parameters: if there are multiple measurements within a visit window, 
 i. The measurement closest to the target day will be used; or ii. If there are multiple measurements within the same distance from the target day, the latest measurement will be used. iii. For tables of extreme lab measurements based on ULN or LLN, convert the lab measurements into times of ULN or LLN first, and then select the extreme measurement. 			

Derived Variables
 
 1. Age (in years) at first dose date 
Obtain age at screening (in days) in yy mm format (e.g., 24 years, 6 months) from screening vital signs page, and add 0.5 month to convert to days.
			

Table 11-4 Analysis Visit Windows for Safety and Efficacy Assessments			
Assessment	Visit^a	Target Study Day^b	Analysis Visit Window (in study days)

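### In Part D, a protocol-compliant Period 2 visit on Day 33 is windowed as Day 29 and lost from the washout analysis

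*Protocol*

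**What the plan says.** **Visit timing.** Protocol Table 3-6 allows the Part D Day 29 visit 2 days either side of its target. Footnote d adds: "The Period 2 Visit will occur 6 to 10 days after the actual date of the Day 29 Visit". The dosing footnote in the same table says: "The last dose of VX-445 or placebo in Period 1 will be the morning dose on the Day 29 Visit". From then until the Period 2 visit, active-arm subjects take TEZ/IVA without VX-445. The protocol's design rationale (Section 9.3.1.2) says Period 2 is there to study exposure-response while VX-445 washes out.

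**Analysis windows.** SAP Appendix B, Table 11-4, gives the Period 2 target as "Period 2 visit (36"). For Part D spirometry and sweat chloride, the entries for Day 29, Period 2 and Safety Follow-up end with "22, 33] (33, 50] Use nominal visit". So Days 23 to 33 are Day 29 and Days 34 to 50 are Period 2. Only Safety Follow-up is assigned by nominal visit. The notes to the table say: "The analysis visit windows will be applied using the following rules for both scheduled and unscheduled visits". For efficacy parameters, "if there are multiple measurements within a visit window, the measurement at the scheduled visit will be used"; failing that, the value closest to the target day is taken. A visit with no measurement in its window is treated as missing.

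**Analyses that use these labels.** The Period 2 analyses of ppFEV1 (SAP Section 8.3.1.3.1) and sweat chloride (Section 8.3.5.3) are ANCOVAs at the single Period 2 visit. The primary model (Section 8.3.1.1.1) and the sweat chloride models average Days 15 and 29.

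**The concern.** The cut between the two windows lies one day too late for the protocol's own calendar. Day 33 can be a compliant Period 2 visit but cannot be a compliant Day 29 visit, yet the SAP calls it Day 29. Because windows also govern scheduled visits and Period 2 has no nominal-visit exception, nothing in the table rescues the record.

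Two things are at stake. First, with a single post-Period 1 visit in the ANCOVA, a subject whose only Period 2 value falls on Day 33 drops out of that analysis altogether. Second, if the Day 29 visit produced no valid value, a measurement taken 6 days after the last VX-445 dose could be used as the Day 29 value.

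**Working it through.** **Inputs.** Day 29 visit on Day 27 to 31 and Period 2 visit 6 to 10 days later (protocol Table 3-6). Target days 29, 36 and 64, and the windows (22, 33] and (33, 50] (SAP Table 11-4, Parts D1 and D2).

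**Reproducing the SAP's bounds.** They match the midpoint of adjacent target days, with halves rounded up:

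- Part D Day 29 to Period 2: (29 + 36)/2 = 32.5, rounded to 33.
- Part D Period 2 to Safety Follow-up: (36 + 64)/2 = 50.
- Part E Day 29 to Day 43: (29 + 43)/2 = 36.
- Part F Day 29 to Safety Follow-up: (29 + 57)/2 = 43.

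The rounding causes the problem. Day 33 is 33 − 29 = 4 days from the Day 29 target but 36 − 33 = 3 days from the Period 2 target, so it is nearer to Period 2.

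**Compliant Period 2 days.** Period 2 day = Day 29 visit day + gap.

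| Day 29 visit on | Period 2 visit on | Of these, Day 33 or earlier |
|---|---|---|
| Day 27 | Days 33–37 | 1 (Day 33) |
| Day 28 | Days 34–38 | 0 |
| Day 29 | Days 35–39 | 0 |
| Day 30 | Days 36–40 | 0 |
| Day 31 | Days 37–41 | 0 |

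There are 5 × 5 = 25 combinations, and 1 (27 + 6 = 33) falls in the Day 29 window. The other 24 fall correctly in (33, 50].

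**When the Day 27 value exists.** Two values then lie in the Day 29 window. If the scheduled-visit rule is read as meaning the Day 29 visit, that value is kept. If both visits count as scheduled, distance decides: |27 − 29| = 2 against |33 − 29| = 4, so the Day 27 value is again kept. For vital signs and pulse oximetry the closest-to-target rule gives the same result. Day 29 is unaffected and the Day 33 value is not used. Unless another measurement lies in (33, 50], Period 2 is missing for that subject.

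**When the Day 27 value is missing or invalid.** Footnote d counts from the actual Day 29 visit, so that visit must have taken place. A missing value is still possible: SAP Section 8.3.5 sets sweat chloride to missing when the volume is below 15 µL or the result is below 10 or above 160 mmol/L. Table 11-4 then makes the Day 33 value the Day 29 value.

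**Scale of that second case.** The smallest arm is TC-low, planned at 9. One subject is 1/9 = 11% of it, and Day 29 is one of two visits averaged. As a rough guide that ignores the model's covariance adjustment, one such value shifts the arm's average by (1/9) × (1/2) = 1/18 of the gap between that subject's Day 33 value and the on-VX-445 value it replaces.

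**After a cut at Day 32.** With (22, 32] and (32, 50], 0 of 25 compliant Period 2 combinations fall in the Day 29 window, and every compliant Day 29 visit (Days 27 to 31) stays inside it.

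**The case against.** The strongest reply is that this is one boundary day and one combination in 25, that a valid Day 29 value is always kept, and that only a supportive analysis loses a record. That stands as to size.

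A second reply is that the SAP already keeps Period 2 values out of the primary analysis. Section 8.3 limits efficacy analyses to measurements up to the final planned visit on treatment, and Section 8.3.1.1.1 limits the primary model to Period 1 visits. This stands in part. Those passages can be read as excluding a Period 2 record. However, the Part D Treatment Period comprises both dosing periods, Section 8.3 defers to the Appendix B windows, and the SAP does not say which governs once Table 11-4 has relabelled the record as Day 29.

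A third reply is that windows must also serve late visits. VX-445 dosing ends at the Day 29 visit, not on calendar Day 29, and spirometry precedes that dose. A Day 29 visit held late on Day 33 would therefore still give an on-VX-445 value. This also stands, and it bears on the choice of fix.

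A reader might infer that the Part F Day 29 efficacy window, (22, 43], is a similar error because it runs well past Day 29. The documents do not support this. The bound is the ordinary midpoint of 29 and 57, and it is longer than in Part D because Part F has no Period 2 visit. Apart from a late Day 29 visit, no scheduled assessment of a completer falls on Days 32 to 43: Safety Follow-up is 28 ± 7 days after the last dose, so at the earliest Day 27 + 21 = 48, and it is assigned by nominal visit. Values from subjects who stopped treatment early are deliberately retained by Section 8.3.

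**Conclusion.** The Part D point holds and is minor. A stated analysis rule mislabels a visit that the protocol permits. The certain consequence is that this washout record is lost from the Period 2 ANCOVAs and from the Period 2 summaries of vital signs and pulse oximetry. This assumes that no other measurement for that subject lies in (33, 50].

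The size is 1 of 25 compliant combinations. That is a count of calendar possibilities, not a probability: the documents do not say how visits are distributed over the allowed days, so the expected number of subjects cannot be given.

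A reader might also infer that off-VX-445 values contaminate the primary ppFEV1 analysis. The documents do not support that as a general statement. It needs a Day 29 visit on Day 27, a missing or invalid value at that visit, a Period 2 visit exactly 6 days later, and a reading of the SAP in which Table 11-4 overrides the Period 1 limit.

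**What to change.** In SAP Table 11-4, assign the Part D Period 2 visit by nominal visit for spirometry, sweat chloride, vital signs and pulse oximetry. This is the preferred change because it also keeps a late, on-VX-445 Day 29 visit on Day 33 out of Period 2. Its cost is that an unscheduled measurement could no longer fill a missing Period 2 value.

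Alternatively, set the Part D windows to (22, 32] for Day 29 and (32, 50] for Period 2. The small downside is that a late, out-of-window Day 29 visit on Day 33 would then be labelled Period 2.

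With either change, add one sentence to the table notes or to Section 8.3 saying that measurements from the Period 2 visit are not used for Day 29. That settles which rule governs. The whole change is a table edit and a sentence, best made before the data cut for the first interim analysis. The Part F window needs no change on this account.

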CFTR	CF transmembrane conductance regulator gene
CFTR	CF transmembrane conductance regulator protein
C _{max}	maximum observed concentration
C _{trough}	predose concentration
CPAP	clinical pharmacology analysis plan
CRF	case report form
CRO	clinical research organization
CRU	clinical research unit
CSR	clinical study report
CYP	cytochrome P450
█	█
ECG	electrocardiogram
EDC	electronic data capture
EENT	eyes, ears, nose, and throat
E _{max}	maximum effect
E-R	exposure-response
ETT	early termination of treatment
EU	European Union
F508del	CFTR gene mutation with an in-frame deletion of a phenylalanine codon corresponding to position 508 of the wild-type protein
F508del	CFTR protein lacking the phenylalanine normally found at position 508 of the wild-type protein
F/F	F508del/F508del genotype
F/MF	F508del /minimal function genotypes
FAS	full analysis set
FDA	Food and Drug Administration
FDC	fixed-dose combination
FEF _{25%-75%}	forced expiratory flow, midexpiratory phase
FEV ₁	forced expiratory volume in 1 second
FSH	follicle-stimulating hormone

Abbreviation	Definition
FVC	forced vital capacity
G6PD	glucose-6-phosphate dehydrogenase
GCP	Good Clinical Practice
GGT	gamma-glutamyl transpeptidase
GLI	Global Lung Function Initiative
GLP	Good Laboratory Practice
GPS	Global Patient Safety (Vertex)
HBE	human bronchial epithelial
HBsAg	hepatitis B surface antigen
HCV	hepatitis C virus
HED	human equivalent dose
HIPAA	Health Insurance Portability and Accountability Act
HIV-1/HIV-2 Abs	antibodies against human immunodeficiency viruses 1 and 2
HR	heart rate
IA	interim analysis
ICF	informed consent form
ICH	International Conference on Harmonization
IDMC	independent data monitoring committee
IEC	independent ethics committee
IPD	important protocol deviation
IRB	institutional review board
IV	intravenous
IVA	ivacaftor
IWRS	interactive web response system
LLN	lower limit of normal
LUM	lumacaftor
max	maximum
MCP	multiple comparisons procedure
MedDRA	Medical Dictionary for Regulatory Activities
MF	minimal function
min	minimum
MMRM	mixed-effects model for repeated measures
n	number of subjects
NOAEL	no-observed-adverse-effect level
NOEL	no-observed-effect level
OATP1B1	organic anion transporting polypeptide 1B1
P	probability
PD	pharmacodynamic, pharmacodynamics
PE	physical examination
PK	pharmacokinetic, pharmacokinetics
ppFEV ₁	percent predicted forced expiratory volume in 1 second
PR	PR interval
q12h	every 12 hours

Abbreviation	Definition
QC	quality control
qd	once daily
QRS	portion of an ECG comprising the Q, R, and S waves, together representing ventricular depolarization
QTc	QT interval corrected
QTcB	QT interval corrected by Bazett's formula
QTcF	QT interval corrected by Fridericia's formula
RR	interval from the onset of 1 QRS complex to the next
SAE	serious adverse event
SAP	statistical analysis plan
SD	standard deviation
SE	standard error
SET	study execution team
SI	International System
SUSAR	suspected, unexpected, serious adverse reaction
TBD	to be determined
TC	triple combination
TC2	triple combination 2 (VX-445/TEZ/VX-561)
TEAE	treatment-emergent adverse event
TEZ	tezacaftor
ULN	upper limit of normal
US	United States
UV	ultraviolet
Vertex	Vertex Pharmaceuticals Incorporated
WHO-DDE	World Health Organization-Drug Dictionary Enhanced

5 INTRODUCTION

5.1 Background

Cystic fibrosis (CF) is an autosomal recessive chronic disease with serious morbidities and frequent premature mortality. At present, there is no cure. CF affects approximately 70,000 individuals worldwide¹ (approximately 30,000 in the US^{1,2} and 32,000 in the EU).³ Based on its prevalence, CF qualifies as an orphan disease.^{4,5}

CF is caused by reduced quantity and/or function of the CFTR (CF transmembrane conductance regulator) protein due to mutations in the *CFTR* gene. The CFTR protein is an epithelial chloride channel that aids in regulating salt and water absorption, and secretion and pH balance in sweat glands and multiple organs, including the lungs, pancreas, and other gastrointestinal organs. Despite progress in the treatment of CF with antibiotics and mucolytics, the predicted median age of survival for a person with CF is approximately 40 years.^{2,6,7} Progressive loss of lung function is the leading cause of mortality.⁸ More effective treatments are needed for CF.

More than 2000 mutations of the *CFTR* gene have been identified.⁹ Most of these mutations are not associated with CF disease or are very rare. Currently, the CFTR2 database contains information on only 322 of these identified mutations, with sufficient evidence to define 281 mutations as disease-causing.¹⁰ The most common disease-causing CFTR mutation, *F508del-CFTR*, accounts for 70% of the identified alleles in patients with CF; nearly half of all people with CF are homozygous for *F508del*.

Based on the understanding of the molecular defects caused by *CFTR* mutations, 2 complementary approaches have been developed to address the decreased quantity and/or function of CFTR in order to enhance chloride transport in patients with CF. Correctors facilitate cellular processing and trafficking to increase the quantity of functional CFTR at the cell surface. Potentiators increase the channel open probability of the CFTR protein delivered to the cell surface to enhance ion transport. Depending on the amount of residual CFTR channel activity in the membrane and the pathophysiology of that activity (reflecting the CFTR genotype of the patient and possibly other factors), both approaches may be required to ameliorate lung disease in patients with CF.

The therapeutic activity of CFTR correctors and potentiators has been established with products that were developed by Vertex Pharmaceuticals Incorporated (Vertex) and approved for the treatment of CF: ivacaftor (IVA) monotherapy (Kalydeco[®]) and lumacaftor (LUM) in combination with IVA (Orkambi[®]). Kalydeco and Orkambi are approved to treat CF in patients with specific *CFTR* genotypes. Tezacaftor (TEZ; VX-661), like LUM, is a first-generation CFTR corrector that improves the processing and trafficking of the F508del-CFTR protein, resulting in an increase in the quantity of F508del-CFTR protein at the cell surface. IVA increases the open-channel probability of the F508del-CFTR protein that has been delivered to the cell surface by TEZ, thereby enhancing total chloride transport. The combined effect of TEZ and IVA is increased quantity and function of F508del-CFTR at the cell surface.

VX-445 is a next-generation CFTR corrector. In vitro, VX-445 improves the processing and trafficking of F508del-CFTR, thereby increasing the quantity of functional F508del-CFTR protein at the cell surface.¹¹ The effect of VX-445 was additive to the effect of TEZ. The CFTR protein delivered to the cell surface by VX-445 alone or in combination with TEZ

(VX-445/TEZ) was potentiated by IVA.¹¹ In human bronchial epithelial (HBE) cells studied in vitro, the triple combination (TC) of VX-445, TEZ, and IVA (VX-445/TEZ/IVA) increased CFTR chloride transport more than any of the dual combinations (VX-445/TEZ, VX-445/IVA, and TEZ/IVA) or individual (VX-445, TEZ, and IVA) regimens.¹¹

VX-561 (also known as CTP-656 or C-10355) is a deuterated isotope of IVA with a specific pattern of 9 substituted deuteriums. In vitro data indicate similar potency of VX-561 in HBE cells relative to IVA. Safety pharmacology and nonclinical toxicology studies of VX-561 demonstrate a similar safety profile relative to IVA. Phase 1 clinical studies in healthy subjects have shown that VX-561 had a reduced rate of clearance, increased exposure, greater plasma levels at 24 hours, and a longer half-life compared to IVA, thereby supporting once daily dosing.¹²

